12.5.2 Safety endpoints

For all safety analyses, the safety set will be used. All listings and tables will be presented by treatment group.

Safety summaries (tables, figures) include only data from the on-treatment period with the exception of baseline data which will also be summarized where appropriate (e.g. change from baseline summaries). In addition, a separate summary for death including on treatment and post treatment deaths will be provided. In particular, summary tables for AEs will summarize only on-treatment events, with a start date during the on-treatment period (treatment-emergent AEs).

The overall observation period will be divided into three mutually exclusive segments:

1. Pre-treatment period: from day of subject's informed consent to the day before first dose of study medication
2. On-treatment period: from day of first dose of study medication to 130 days after last dose of study medication
3. Post-treatment period: starting at day 131 after last dose of any component of the study treatment.

12.5.2.1 Adverse events

Summary tables for AEs will include only AEs that started or worsened during the on-treatment period, the treatment-emergent AEs.

The incidence of treatment-emergent AEs (new or worsening from baseline) will be summarized by system organ class and/or preferred term, severity (based on CTCAE v5.0) and relationship to study treatment.

SAE, non-serious AEs and AESI during the on-treatment period will be tabulated. AESIs will be defined based on the case retrieval strategy (CRS) available at the time of the analysis.

All deaths (on-treatment and post-treatment) will be summarized overall and separately.

All AEs, deaths and SAEs (including those from the pre and post-treatment periods) will be listed and those collected during the pre-treatment and post-treatment period will be flagged.

12.5.2.2 Clinical laboratory evaluations

Grading of laboratory values will be assigned programmatically as per NCI CTCAE version 5.0. The calculation of CTCAE grades will be based on the observed laboratory values only, clinical assessments will not be taken into account.

CTCAE v5.0 Grade 0 will be assigned for all non-missing values not graded as 1 or higher. Grade 5 will not be used.

For laboratory tests where grades are not defined by CTCAE v5.0, results will be categorized as low/normal/high based on laboratory normal ranges.

The following summaries/listings will be generated separately for hematology, and biochemistry tests:

- Listing of all laboratory data with values flagged to show the corresponding CTCAE v5.0 grades if applicable and the classifications relative to the laboratory normal ranges

For laboratory tests where grades are defined by CTCAE v5.0:

- Worst post-baseline CTCAE grade (regardless of the baseline status). Each subject will be counted only once for the worst grade observed post-baseline
- Shift tables using CTCAE v5.0 grades to compare baseline to the worst on-treatment value

For laboratory tests where grades are not defined by CTCAE v5.0:

- Shift tables using the low/normal/high/ (low and high) classification to compare baseline to the worst on-treatment value.

In addition to the above mentioned tables and listings, other exploratory analyses, for example, figures plotting time course of raw or change in laboratory tests over time or box plots might be specified in the analysis plan.

12.5.2.3 Other safety evaluations

Vital signs

All vital signs data will be listed by treatment group, subject, and visit/cycle. Notable values will be flagged.

Immunogenicity

Immunogenicity of canakinumab and pembrolizumab will be characterized descriptively by tabulating ADA prevalence at baseline and ADA incidence on-treatment.

12.5.3 Pharmacokinetics

PAS will be used in the pharmacokinetic data analysis. Descriptive statistics (n, m (number of non-zero concentrations), mean, coefficient of variation in percent (CV%), SD, median, geometric mean, geometric CV%, minimum and maximum) for canakinumab and pembrolizumab concentrations will be presented at each scheduled timepoint separately.

All concentration data for canakinumab and pembrolizumab vs. time profiles will be displayed graphically.

12.5.3.1 Population pharmacokinetic analysis

If there is adequate amount of data, a mixed-effects model may be applied to the serum canakinumab concentration-time data from this study along with other studies to generate posthoc estimates of pharmacokinetic parameters using NONMEM to characterize canakinumab exposure and to determine the effects of intrinsic (i.e. demographic factors) and extrinsic covariates (e.g. combination partners) on canakinumab exposure. If there is sufficient data for analysis, the details of the population pharmacokinetic analyses may be provided in a separate reporting and analysis plan, and the results may be reported in a separate population pharmacokinetic report. Similarly, population PK analysis may also be applied to pembrolizumab to determine the effects of canakinumab on pembrolizumab.

12.5.4 Biomarkers

The secondary objective related to biomarker is to assess the relationship between key blood or tissue based biomarkers and MPR. FAS will be used for biomarker related analyses.

The relationship between key IHC markers (PD-L1, CD8), key cytokines (hs-CRP and hs-IL-6) assessed at baseline and post-baseline and MPR will be explored. MPR will be summarized by treatment arm and subgroup along with the two-sided exact binomial 95% confidence interval ([Clopper and Pearson E. 1934](#)). The threshold used for the markers will be specified in SAP. In addition, baseline and changes from baseline for the IHC markers and cytokines (absolute change, percent change and fold change) at each time point will be summarized in tables that include sample size, mean, standard deviation, CV%, median, minimum and maximum. For fold change from baseline, geometric mean and geometric CV% will also be included.

All biomarker data will also be listed.

12.7 Interim analyses

Not applicable.

12.8 Sample size calculation

12.8.1 Primary endpoint(s)

A MPR of approximately 20% can be achieved using chemotherapy ([Pataer 2012](#)). A 10% absolute improvement to 30% and a 25% absolute improvement to 45% in MPR rate are considered clinically meaningful minimum improvement in canakinumab alone arm and canakinumab in combination with pembrolizumab arm, respectively.

Approximately 110 subjects will be randomized in a 2:2:1 ratio to one of the treatment arms (canakinumab alone or canakinumab in combination with pembrolizumab or pembrolizumab alone). The proof of efficacy in each treatment arm will be determined by Bayesian double criteria.

Among the 44 subjects randomized to canakinumab single agent treatment, at least 14 responders are needed to meet the proof of efficacy criteria. When the true MPR rate is $\leq 20\%$, the probability of erroneously declaring proof of efficacy is at most 4.4%, while the probability of declaring proof of efficacy is at least 89.8% for $\text{MPR} \geq 40\%$ ([Table 12-1](#)).

Among the 44 subjects randomized to the canakinumab and pembrolizumab combination treatment, at least 20 responders are required to meet the proof of efficacy criteria. When the true MPR rate is $\leq 30\%$, the probability of erroneously declaring proof of efficacy is at most 2.1% while the probability of declaring proof of efficacy is at least 92.2% for $\text{MPR} \geq 55\%$ ([Table 12-2](#)). Assuming an enrollment rate of 6 subjects per month, the enrollment will be completed at approximately 18 months and MPR assessment for the last patient randomized will occur at approximately 20 months from the date of first subject randomized in the study.

Table 12-1 Operating characteristics with 44 subjects randomized to canakinumab treatment arm

True MPR	Probability of declaring proof of efficacy (14 or more responders)	Probability of missing proof of efficacy (13 or less responders)
20%	4.4%	95.6%
30%	45.2%	54.8%
40%	89.8%	10.2%
50%	99.5%	0.5%

Table 12-2 Operating characteristics with 44 subjects randomized to the canakinumab + pembrolizumab combination treatment arm

True MPR	Probability of declaring proof of efficacy (20 or more responders)	Probability of missing proof of efficacy (19 or less responders)
30%	2.1%	97.8%
40%	27.7%	72.3%
45%	53.4%	46.6%
55%	92.2%	7.8%

13 Ethical considerations and administrative procedures

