12.4.2 Statistical model, hypothesis, and method of analysis

The primary endpoint analysis will be described by the following five attributes:

1. The **target population** is defined as all randomized patients who are histologically confirmed NSCLC stage IB-IIIA (per AJCC 8th edition), deemed suitable for primary resection by treating surgeon, except for N2 and T4 tumors.
2. The **primary variable** is the percentage of subjects with a major pathological response (defined as $\leq 10\%$ residual viable cancer cells per central review). Any patient who has $>10\%$ residual viable cancer cells, or starts new antineoplastic therapy medication prior to surgery, or does not have the surgery performed, is considered as a non-responder.
3. The **study treatment** is canakinumab as monotherapy or in combination with pembrolizumab.
4. The **intercurrent events** of interest in this study are: start of new antineoplastic therapy prior to surgery and discontinuation of study treatment prior to surgery. These intercurrent events will be addressed as follows:
 - a. **Start of new antineoplastic therapy prior to surgery:** subject will be considered as non-responder (composite strategy)
 - b. **Discontinuation of study treatment prior to surgery:** subject will be included in the analysis regardless of this intercurrent event (treatment-policy strategy).
5. The **summary measure** is MPR rate with its corresponding two-sided exact binomial 95% confidence interval ([Clopper and Pearson E. 1934](#)) in canakinumab alone arm and canakinumab in combination with pembrolizumab arm.

A MPR of approximately 20% can be achieved using chemotherapy ([Pataer 2012](#)). For canakinumab alone arm, a 10% absolute improvement in the MPR to 30% is considered a clinically meaningful minimum improvement in this study population. Therefore, proof of efficacy in canakinumab alone arm will be declared if both of the following conditions are met:

- the mean of the posterior distribution of MPR is at least 30% and
- the posterior probability that the MPR is $\geq 20\%$ is at least 90%

For the combination of canakinumab and pembrolizumab treatment arm, a 25% absolute improvement in the MPR to 45% is considered a clinically meaningful minimum improvement in this study population. Therefore, proof of efficacy in the combination treatment arm will be declared if both of the following conditions are met:

- the mean of the posterior distribution of MPR is at least 45% and

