- the posterior probability that the MPR is $\geq 30\%$ is at least 90%

The posterior distribution of MPR will be derived from the prior distribution and all available data from the subjects included in the FAS. A minimally informative unimodal Beta prior ([Neuenschwander et al 2008](#)) will be used for MPR in each arm. Details of prior distribution will be specified in the SAP.

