For the combination of canakinumab and pembrolizumab treatment arm, a 25% absolute improvement in the MPR to 45% is considered a clinically meaningful minimum improvement in this study population. Therefore, proof of efficacy in the combination treatment arm will be declared if both of the following conditions are met:

- the mean of the posterior distribution of MPR is at least 45% and
- the posterior probability that the MPR is  $\geq 30\%$  is at least 90%

The posterior distribution of MPR will be derived from the prior distribution and all available data from the subjects in the FAS. A minimally informative unimodal Beta prior ([Neuenschwander et al 2008](#)) Beta(3/7, 1) and Beta(9/11, 1) will be used for canakinumab monotherapy and canakinumab in combination with pembrolizumab, respectively. Please refer to [Section 5.4.1](#) for details of prior distribution. The posterior mean of MPR will be calculated and the MPR rate with its corresponding two-sided exact binomial 95% confidence interval ([Clopper CJ and Pearson ES \(1934\)](#)) will be estimated in both the canakinumab monotherapy arm and canakinumab in combination with pembrolizumab arm. The posterior probability that  $MPR \geq 20\%$  and the posterior probability that  $MPR \geq 30\%$  will be calculated for canakinumab monotherapy arm and canakinumab in combination with pembrolizumab arm, respectively. Waterfall plot for percentage of residual viable tumor based on central review in canakinumab monotherapy arm and canakinumab in combination with pembrolizumab arm will be generated.

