**Table 3-1      Operating characteristics with 44 subjects randomized to canakinumab treatment arm**

True MPR	Probability of declaring proof of efficacy (12 or more responders)	Probability of missing proof of efficacy (11 or less responders)
20%	4.4%	95.6%
30%	45.2%	54.8%

True MPR	Probability of declaring proof of efficacy (12 or more responders)	Probability of missing proof of efficacy (11 or less responders)
40%	89.8%	10.2%
50%	99.5%	0.5%

**Table 3-2 Operating characteristics with 44 subjects randomized to the canakinumab + pembrolizumab combination treatment arm**

True MPR	Probability of declaring proof of efficacy (20 or more responders)	Probability of missing proof of efficacy (19 or less responders)
30%	2.1%	97.8%
40%	27.7%	72.3%
45%	53.4%	46.6%
55%	92.2%	7.8%

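### The combination arm's stated false-positive maximum of 2.1% should be 2.2%: 20 or more responders of 44 at a true rate of 30% has probability 2.18%

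*Protocol*

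**What the plan says.** Protocol section 12.8.1 gives the operating characteristics of the Bayesian double criterion for each of the two canakinumab arms. The combination-arm statement begins "Among the 44 subjects randomized to the canakinumab and pembrolizumab combination treatment" and continues that "at least 20 responders are required to meet the proof of efficacy criteria". For true MPR rates up to and including 30%, it states that "the probability of erroneously declaring proof of efficacy is at most 2.1" per cent. Protocol Table 12-2 repeats this in its 30% row, with 2.1% for declaring proof of efficacy (20 or more responders) and 97.8% for missing it (19 or fewer).

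SAP section 3.1 carries the same sentence. SAP Table 3-2, titled "Operating characteristics with 44 subjects randomized to the canakinumab + pembrolizumab combination treatment arm", carries the same row.

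The cutoff of 20 comes from the decision criteria in Protocol section 12.4.2: a posterior mean MPR of at least 45%, and a posterior probability of at least 90% that MPR is 30% or more. SAP section 2.5.2 fixes the priors: "Beta(3/7, 1) and Beta(9/11, 1) will be used for canakinumab monotherapy and canakinumab in combination with pembrolizumab, respectively".

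**The concern.** The two probabilities in a row of Table 12-2 belong to complementary events, so they should add to 100% apart from rounding. At 30% they add to 99.9%, while every other row in Protocol Tables 12-1 and 12-2 adds to 100.0%. One of the two entries is therefore suspect. If it is the 2.1%, the same figure in the text is also wrong, and there it is worded as a maximum.

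Little is at stake in size. But this is the only false-positive probability that the plan gives for the combination arm, and the misprint makes the design look slightly stricter than it is. A reader who recomputes the table will find that this entry does not reproduce, and may then doubt the other entries, which do.

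**Working it through.** **Inputs**

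- Combination arm size: n = 44 (Protocol 12.8.1).
- Success rule: 20 or more responders (Protocol 12.8.1, Table 12-2).
- Boundary of the null range: true MPR p = 0.30 (Protocol 12.8.1).
- Prior: Beta(9/11, 1) (SAP 2.5.2).

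**Step 1: is 20 the right cutoff?** With y responders the posterior is Beta(9/11 + y, 1 + 44 − y), with mean (9/11 + y) / (9/11 + 45).

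- y = 19: 19.818 / 45.818 = 0.4325, below 0.45.
- y = 20: 20.818 / 45.818 = 0.4544, at or above 0.45.
- At y = 20 the posterior probability that MPR is 30% or more is 98.5%, above the required 90%.

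So 20 is the smallest number that meets both criteria, as the plan states.

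**Step 2: the false-positive probability.** The probability of 20 or more responders rises with p, so its maximum over p ≤ 0.30 is at p = 0.30:

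P(X ≥ 20) = Σ (k = 20 to 44) C(44, k) × 0.30^k × 0.70^(44 − k) = 0.021757

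P(X ≤ 19) = 1 − 0.021757 = 0.978243

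To one decimal these are 2.2% and 97.8%, which add to 100.0%. The printed 97.8% is right and the printed 2.1% is not.

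**Step 3: do the other entries reproduce?** Exact values against those printed in the Protocol:

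| Table | True MPR | Declare: exact | Declare: printed | Miss: exact | Miss: printed |
|---|---|---|---|---|---|
| 12-1 (≥14 of 44) | 20% | 4.365% | 4.4% | 95.635% | 95.6% |
| 12-1 | 30% | 45.207% | 45.2% | 54.793% | 54.8% |
| 12-1 | 40% | 89.789% | 89.8% | 10.211% | 10.2% |
| 12-1 | 50% | 99.522% | 99.5% | 0.478% | 0.5% |
| 12-2 (≥20 of 44) | 30% | **2.176%** | **2.1%** | 97.824% | 97.8% |
| 12-2 | 40% | 27.734% | 27.7% | 72.266% | 72.3% |
| 12-2 | 45% | 53.414% | 53.4% | 46.586% | 46.6% |
| 12-2 | 55% | 92.246% | 92.2% | 7.754% | 7.8% |

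Fifteen of the 16 entries match ordinary rounding. Truncation would turn 2.176% into 2.1%, but it would also print 4.3% for 4.365%, 89.7% for 89.789% and 7.7% for 7.754%, and the tables do not do that.

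**Step 4: could 2.1% come from another calculation at p = 0.30?**

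- Normal approximation: 1.26%; with continuity correction: 1.91%.
- 20 or more of 43: 1.64%; 20 or more of 45: 2.83%.
- 19 or more of 44: 4.37%; 21 or more of 44: 1.00%.

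None of these gives 2.1%.

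**The case against.** The case for leaving this alone is that it has no consequence. The gap is 2.176 − 2.1 = 0.076 percentage points. Success is judged on the posterior mean and the posterior probability, so the 2.1% enters no decision rule, error allocation or planned analysis.

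The figure is also nominal. SAP section 1 records that recruitment was halted, and SAP section 5.4.1 says the criteria are applied to the number actually enrolled. If the smallest qualifying number of responders is recalculated for each arm size, the probability at a true rate of 30% is 1.99% for 41 subjects, 2.64% for 42, 1.64% for 43, 2.18% for 44, 1.35% for 45 and 1.80% for 46. The actual arm size is not in the documents, so this range is only illustrative, but a change of one subject matters several times more than the misprint.

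Finally, the wording of a maximum can be read as saying only that the worst case lies at the 30% boundary. On a strict reading, the companion claim of at least 89.8% for the canakinumab-alone arm also fails, since the exact value is 89.789%.

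Most of this stands. The error is immaterial to the design, and the case should not rest on the words about a maximum alone. What the objection does not do is make 2.1% correct. The text fixes 44 subjects and a cutoff of 20. The 89.8% is a properly rounded value and the 2.1% is not, and the 2.1% contradicts the entry beside it.

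**Conclusion.** The concern holds. Under the rule, arm size and null boundary that the plan states, the maximum false-positive probability for the combination arm is 2.18%, or 2.2% to one decimal, against a printed 2.1%. The only modelling assumption is that responders in the arm follow a binomial distribution with a common true rate, which the other 15 entries in the two Protocol tables confirm is how they were calculated.

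This is a last-digit error of about 0.08 percentage points. It leaves the cutoff of 20, the sample size, the posterior criteria, the power figures and the conclusions unchanged, and it belongs at the lowest level of importance.

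The statement that the remaining entries reproduce covers Protocol Tables 12-1 and 12-2. SAP Table 3-1 prints the Table 12-1 percentages under column headings of 12 or more and 11 or fewer responders. That is a separate discrepancy, and nothing here clears it.

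**What to change.** Change 2.1% to 2.2% in four places: the text of Protocol section 12.8.1, the 30% row of Protocol Table 12-2, the text of SAP section 3.1, and the 30% row of SAP Table 3-2. The corrected row reads 2.2% and 97.8% and adds to 100.0%. Because 2.176% is below 2.2%, the sentence then also holds as a maximum. The Protocol's amendment summary repeats the old figure, but as a record of past changes it need not be altered.

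The cost is one figure in four places and a very slightly less favourable stated error rate. No analysis, program or decision rule needs to change.

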13.1 Regulatory and ethical compliance

This clinical study was designed and shall be implemented, executed and reported in accordance with the ICH Harmonized Tripartite Guidelines for GCP, with applicable local regulations (including European Directive 2001/20/EC, US CFR 21), and with the ethical principles laid down in the Declaration of Helsinki.

13.2 Responsibilities of the investigator and IRB/IEC

Before initiating a trial, the investigator/institution must obtain approval/favorable opinion from the IRB/IEC for the trial protocol, written ICF, consent form updates, subject recruitment procedures (e.g. advertisements) and any other written information to be provided to subjects. Prior to study start, the investigator is required to sign a protocol signature page confirming his/her agreement to conduct the study in accordance with these documents and all of the instructions and procedures found in this protocol and to give access to all relevant data and records to Novartis monitors, auditors, Novartis Quality Assurance representatives, designated agents of Novartis, IRBs/IECs, and regulatory authorities as required. If an inspection of the clinical site is requested by a regulatory authority, the investigator must inform Novartis immediately that this request has been made.

13.3 Publication of study protocol and results

The protocol will be registered in a publicly accessible database such as clinicaltrials.gov and as required in EudraCT. In addition, after study completion (defined as last patient last visit) and finalization of the study report the results of this trial will be submitted for publication and

posted in a publicly accessible database of clinical trial results, such as the Novartis clinical trial results website and all required Health Authority websites (e.g. Clinicaltrials.gov, EudraCT etc.).

For details on the Novartis publication policy including authorship criteria, please refer to the Novartis publication policy training materials that were provided to you at the trial investigator meetings.

13.4 Quality Control and Quality Assurance

Novartis maintains a robust Quality Management System (QMS) that includes all activities involved in quality assurance and quality control, to ensure compliance with written Standard Operating Procedures as well as applicable global/local GCP regulations and ICH Guidelines.

Audits of investigator sites, vendors, and Novartis systems are performed by auditors, independent from those involved in conducting, monitoring or performing quality control of the clinical trial. The clinical audit process uses a knowledge/risk based approach.

Audits are conducted to assess GCP compliance with global and local regulatory requirements, protocols and internal Standard Operating Procedures (SOPs), and are performed according to written Novartis processes.

14 Protocol adherence

This protocol defines the study objectives, the study procedures and the data to be collected on study participants. Additional assessments required to ensure safety of subjects should be administered as deemed necessary on a case by case basis. Under no circumstances including incidental collection is an investigator allowed to collect additional data or conduct any additional procedures for any purpose involving any investigational drugs under the protocol, other than the purpose of the study. If despite this interdiction prohibition, data, information, observation would be incidentally collected, the investigator shall immediately disclose it to Novartis and not use it for any purpose other than the study, except for the appropriate monitoring on study participants.

Investigators ascertain they will apply due diligence to avoid protocol deviations. If an investigator feels a protocol deviation would improve the conduct of the study this must be considered a protocol amendment, and unless such an amendment is agreed upon by Novartis and approved by the IRB/IEC and Health Authorities, where required, it cannot be implemented.

